## Abstract

**Objectives:** To determine if early treatment with convalescent plasma (CP) therapy reduces 30-day mortality among Veterans hospitalized at a Department of Veterans Affairs (VA) facility with non-severe COVID-19.

**Research Design:** This is a non-interventional, retrospective data collection study, designed to emulate a (hypothetical) target randomized trial using observational data from the VA electronic health record (EHR) database. Eligible patients will include Veterans admitted to a VA Medical Center with a SARS-CoV-2 positive test within 7 days of admission, had no prior plasma treatment, and non-severe disease. The intervention is CP administered within 2 days of hospitalization and SARS-CoV-2 positive test. The outcome is 30-day all-cause mortality.

**Methodology:** This project will access VA healthcare data in the EHR on a national basis. Data will be identified and captured using Computerized Patient Record System (CPRS), on VHA servers and the Corporate Data Warehouse (CDW) using the VA Informatics and Computing Infrastructure (VINCI) servers and non-identifiable data will be captured using the VA REDCap system. This will also include data from the VA Pathology & Laboratory Medicine Service. Additional data will be provided from the Mayo Clinic CP Registry to identify VA patients who have received CP. Death and morbidity, including intensive care unit (ICU) transition, intubation, extubation, and discharge, will be assessed using VHA data. We will fit inverse probability weighted pooled logistic models to estimate the observational analogue of the per-protocol effect of CP on 30-day mortality with cumulative incidence curves, risk differences, and hazard ratios.

**Clinical Implications:** This project will allow a comprehensive assessment of the impact of convalescent plasma on morbidity and mortality among Veterans with COVID-19. This study aims to produce early evidence on the effectiveness of CP therapy, a promising approach to treating COVID-19. This evidence will help clinicians deliver better clinical care to critically-ill Veterans. In addition, it will set the stage for further research that informs the use of CP in patients with COVID-19.

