## 5.0 Study Procedures

### 5.1 Study Design

This study is an observational study which emulates a hypothetical randomized trial (target trial) using observational data from the VHA EHR database. VA data will be used to emulate the eligibility criteria, treatment strategies, outcome, and follow-up of the target trial.

The specifications of the hypothetical trial are as follows. Patients would include Veterans hospitalized at a VA facility with a first-ever SARS-CoV-2 positive test within 7 days of admission, oxygen saturation of  $\geq 90\%$  within the past day, and non-severe COVID-19. Patients previously treated with convalescent plasma or residing in long-term care in the past 90 days would not be eligible. The patient would become eligible at the first SARS-CoV-2-positive test date (if the positive test occurred during hospitalization) or at the hospital admission date (if the positive test occurred before hospitalization). Eligible patients would be randomly assigned to either receive or not receive CP within 2 days of assignment. The primary outcome is 30-day mortality.

This retrospective data collection study will be conducted at the CSPECs within the VA Boston and VA Puget Sound health care systems. This project will access VA healthcare data in the EHR at a national level. Data will be identified and captured using CPRS, on VHA servers and the CDW using VINCI servers. Approved study staff will have access to the VINCI data mart to identify Veterans with positive SARS-CoV-2 testing.

If necessary, data can be extracted from medical records. In this case, data from VINCI/CDW will be reviewed by study staff and entered into a VA REDCap database. Each subject will be assigned a unique study ID and no PHI will be captured within VA REDCap. A crosswalk will be used to link the study ID to the Patient ICN. This document will be the only document to link study data and will be kept secure within the study's VINCI workspace and will only be accessible to a limited number of study staff conducting data review.

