### **Exposure: CP Treatment**

The primary exposure of interest is the use or the non-use of CP. These data are derived from multiple sources, including the VA Pathology and Laboratory Medicine Service, CDW, and the Mayo Clinic CP Registry. Data on CP recipients from the Mayo Clinic and VA Pathology and Laboratory Medicine Service will be matched to EHR data with unique identifiers, which include name, date of birth, VA patient identifiers (e.g., Patient ICN), date of hospitalization, and VA medical center or hospital. Other identifying information to match records may also be available, such as Social Security Numbers from the VA Pathology and Laboratory Medicine Service. Mayo Clinic data will not include Social Security numbers.

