### **Statistical Analysis Plan**

The target trial to emulate would include US Veterans hospitalized at a VA medical center where CP was a current practice. The patient would become eligible at the first SARS-CoV-2-positive test date (if the positive test occurred during hospitalization) or at the hospital admission date (if the positive test occurred before hospitalization).

Eligible patients would be randomly assigned to either receive or not receive CP. The exact timing of transfusion and determination of suitability for use (based on antibody levels or donor characteristics of the plasma units) would be left to the discretion of treating physicians. The primary outcome would be 30-day mortality. The causal contrasts of interest are the intention-to-treat effect and the per-protocol effect. To estimate the intention-to-treat effect (the effect of assignment to CP on outcomes), estimate the risk difference and hazard ratio comparing patients in the CP and non-CP group. The risk (cumulative incidence) of outcomes could be estimated nonparametrically using the Kaplan-Meier method or under parametric smoothing assumptions via a pooled logistic regression model including a time-varying intercept, an indicator for treatment group, and a product (“interaction”) term between time and treatment group. The hazard ratio could be estimated from the pooled logistic regression model without the product term. In the case of a prespecified imbalance in baseline characteristics between intervention arms, relevant covariates could be added to the model.

To estimate the per-protocol effect (the effect of treatment with CP on outcomes if all patients had adhered to the protocol), we would restrict the above intention-to-treat analysis to patients who adhered to their assigned treatment (CP or no CP) and adjust for the a priori baseline prognostic factors, as well as trial start day relative to first eligibility. The adjustment for these covariates would be carried out via inverse probability weighting, with all continuous variables

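### The CP exposure window is stated inconsistently, CP given after it has no rule, and assignment day is undefined, so immortal time is not ruled out

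*Combined protocol and SAP*

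**What the plan says.** Four places describe the exposure.

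- **Abstract:** "The intervention is CP administered within 2 days of hospitalization and SARS-CoV-2 positive test".
- **Section 5.1, Study Design:** "Eligible patients would be randomly assigned to either receive or not receive CP within 2 days of assignment". For time zero it says "The patient would become eligible at the first SARS-CoV-2-positive test date (if the positive test occurred during hospitalization"; if the test came first, eligibility starts at admission. Time zero is therefore the later of the two dates. The criterion "first-ever SARS-CoV-2 positive test within 7 days of admission" lets them lie up to 7 days apart.
- **Section 5.6, Exposure: CP Treatment:** "The primary exposure of interest is the use or the non-use of CP", with no window.
- **Section 5.6, Statistical Analysis Plan:** "Eligible patients would be randomly assigned to either receive or not receive CP", again with no window. "The exact timing of transfusion and determination of suitability for use" is left to the treating physicians. For the per-protocol effect the SAP would "restrict the above intention-to-treat analysis to patients who adhered to their assigned treatment (CP or no CP"), without saying by when CP must have been given.

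The SAP also adjusts for the interval between first eligibility and the start of the trial. It does not define that start or tie it to transfusion or to a window. No section says how a first transfusion after day 2 is classified, or to which group a patient belongs who dies inside the window before transfusion.

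**The concern.** In a randomised trial the arm is known at assignment. In an emulation it has to be inferred from the transfusion record, so the exposure window is what defines the groups. If the window is open to interpretation, the primary contrast cannot be reproduced from the plan.

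Two kinds of harm are possible. First, the literal Abstract rule leaves some eligible patients with zero probability of CP. Inverse probability weights cannot repair that. Second, a no-window rule followed from first eligibility counts someone transfused on day 10 as CP from day 0, when that person had to survive 10 days to qualify. Weights for baseline covariates do not remove that survival condition. The no-window rule would also no longer address early treatment, which is the stated objective. The Communication Plan foresees weekly analyses, so a definition left open could end up being settled with results in view.

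**Working it through.** **1. Do the rules classify the same patient alike?** Days are counted from admission; time zero z is the later of test and admission. The literal Abstract rule requires transfusion within 2 days of each date. The section 5.1 column takes assignment to be at z.

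| Test day | CP day | Abstract, literal | Section 5.1 | Use / non-use |
|---|---|---|---|---|
| 0 | 1 | CP | CP | CP |
| -5 | 1 | not CP | CP | CP |
| 6 | 7 | not CP | CP | CP |
| 0 | 5 | not CP | not CP | CP |

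Over all whole-day pairs with test from day -7 to 7 and transfusion from z to day 10 (137 pairs), all rules give CP for 9, the two 2-day rules differ on 36, and 92 are CP only with no window. These are counts of combinations, not shares of patients.

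**2. Feasibility under the literal Abstract.** With a gap of g days between test and admission, the last permitted transfusion day is 2 - g after z. It must be at least 0, so g must be 2 or less. Gaps of 3, 4, 5, 6 and 7 days, that is 5 of the 8 possible gaps, can never yield a CP patient. The documents do not give the share of patients with such gaps.

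**3. Immortal time under the no-window reading.** From the plan: 25% mortality (Sample Size/Power), 30 days of follow-up, and one sixth intended for CP (500 of 3,000). Assumed: no CP effect; a share of intended recipients treated late, uniformly on days 3 to 14 and only if still alive; the rest treated on day 0; everyone followed from day 0. The estimate is a Mantel-Haenszel daily hazard ratio, ever versus never CP, in 2,000,000 simulated patients per scenario.

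| Late share (assumed) | Constant hazard | 85% of hazard in first 15 days |
|---|---|---|
| 20% | 0.93 | 0.89 |
| 40% | 0.86 | 0.78 |
| 60% | 0.79 | 0.68 |

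The true value is 1. As a rough yardstick, the hazard ratios of 1.3 to 1.5 in Sample Size/Power invert to 1/1.3 = 0.77 and 1/1.5 = 0.67.

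**4. A 2-day window alone.** With transfusion uniform over days 0 to 2 and pre-transfusion deaths counted as no-CP, the null hazard ratio is still about 0.96 with a constant hazard and 0.91 with a front-loaded one (Weibull shape 0.8). The risk difference is about -1 to -2 percentage points.

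**5. Effect on power.** The plan's figures first. Two-sided alpha 0.05 (sidedness assumed), p0 = 0.25, p1 = 1 - 0.75^HR, and a two-proportion test with n1 exposed and 5 x n1 unexposed:

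power = Φ[(p1 - p0 - 1.96 x se0) / se1], with se0 pooled and se1 unpooled.

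At HR 1.3, p1 = 0.312 and the difference is 0.062. With 500 and 2,500: se0 = 0.0215, se1 = 0.0225, power = Φ(0.885) = 0.81, against the stated 80%. HR 1.35 gives 0.905. With effective N 1,500, HR 1.43 gives 0.802 and HR 1.50 gives 0.893. All four stated figures reproduce.

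The 500 is extrapolated from all 250 known recipients, with no time limit. If an assumed 50% are inside the window (250 and 1,250): se0 = 0.0304, se1 = 0.0318, power at HR 1.3 = Φ(0.076) = 0.53. At an assumed 75% it is 0.70, and at 25% it is 0.31. Keeping 2,500 controls gives 0.57 at 50%. The detectable hazard ratio (80% / 90% power, 5:1, before any design effect) becomes 1.34 / 1.41 at 75%, 1.43 / 1.51 at 50% and 1.63 / 1.75 at 25%.

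**The case against.** A reader might infer that the definitions are flatly incompatible and that the SAP does credit late recipients with immortal time. The documents do not support either statement, for three reasons.

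- The Abstract can be read as 2 days from the moment the patient is both hospitalized and test-positive. That is the section 5.1 time zero. The preceding sentence of the Abstract admits tests up to 7 days from admission, which favours this reading, and the infeasible gaps then disappear.
- The Exposure section mainly describes data sources and record matching. The SAP belongs to the same protocol, so physician discretion over exact timing can mean timing inside the section 5.1 window. Omitting a window is not the same as setting a rival one.
- Adjusting for the delay from first eligibility to trial start makes sense only if starts can fall after first eligibility. With such staggered starts, a patient transfused on day 10 who is still eligible could be assigned shortly before and be validly CP under section 5.1.

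Each of these readings is reasonable and they stand as readings. None is written down, however. The trial start is undefined and is not linked to transfusion, late CP has no rule, and two analysts could reconcile the text differently. Even the most favourable reading leaves deaths inside the window unassigned.

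**Conclusion.** The exposure definition is inconsistent across four sections and incomplete on three points: what fixes the trial start day, how CP after the window is classified, and where deaths before transfusion inside the window are counted. These should be settled before analysis, because the primary contrast depends on them.

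The zero-probability problem for gaps of 3 to 7 days holds only if the Abstract is read literally. Null hazard ratios of about 0.93 to 0.68 hold only with no window and follow-up from first eligibility; they rest on assumed late shares of 20% to 60% and assumed transfusion times and hazard shapes. A smaller bias, about 0.91 to 0.96 under no effect, can remain with a 2-day window if early deaths all go to the no-CP group. The loss of power depends on the share of recipients inside the window, which the documents do not give.

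**What to change.** Reconcile the Abstract, section 5.1, the Exposure section and the SAP to one analytic exposure definition:

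1. Define the assignment (trial start) day and count the window from it. If starts are staggered, say so, apply eligibility at each start, and begin follow-up at that start.
2. State that CP first given after the window does not make a patient CP from that start. The patient is followed as no-CP and censored with weights at transfusion, or enters a later trial start for which he or she is eligible.
3. State how deaths inside the window before transfusion are assigned, so that they do not all fall to no-CP. Cloning, with censoring and weighting over the grace period, is one way.
4. Restate the detectable hazard ratios for the number of recipients who meet the definition.

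The wording changes are small, and the dates should be in the EHR and registry data. The real costs are extra weighting work, since the SAP now plans adjustment only for baseline factors and trial start day, and an exposed group likely to be smaller than 500. The change concerns classification of existing records and prescribes no clinical care.

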## **Acronyms and Abbreviations**

CDW	Corporate Data Warehouse
COVID-19	Coronavirus disease 2019
CP	Convalescent plasma
CSP	Cooperative Studies Program
CPRS	Computerized Patient Record System
CSPCO	Cooperative Studies Program Central Office
CSPEC	Cooperative Studies Program Epidemiology Center
EHR	Electronic health record
ICU	Intensive Care Unit
III	Individually-Identifiable Information
PHI	Protected Health Information
R&D	Research and Development
SARS-CoV-2	Severe Acute Respiratory Syndrome Coronavirus 2
SSN	Social Security Number
VA	Department of Veterans Affairs
VHA	Veterans Health Administration
VINCI	VA Informatics and Computing Infrastructure
VistA	Veterans Health Information Systems and Technology Architecture

**Protocol Title:**

Observational Study of Convalescent Plasma for treatment of Veterans with COVID-19

## 2.0 Introduction

### 2.1 Background

The epidemic of coronavirus disease 2019 (COVID-19) in Wuhan, China disproportionately infected persons who were older, male, and infirm. Mortality risk and adverse outcomes followed the same pattern. Reports from United States have described a similar pattern of affected individuals. Many Veterans fit the vulnerable profile. As of June 15, 2020, 13,984 Veterans have been tested or treated for known or probable COVID-19 at a Department of Veterans Affairs (VA) facility.

### 2.2 Rationale

The convalescent plasma (CP) collected from individuals who have recovered from a viral infection contain neutralizing antibodies. Administering CP to individuals who are infected by the virus may reduce symptoms and mortality. There is some evidence of benefit of CP treatment against respiratory illnesses during previous outbreaks, such as severe acute respiratory syndrome (SARS), novel influenza A subtype H1N1, and avian influenza virus subtype H5N1. Recent data suggest that CP may improve outcomes in patients with COVID-19. Based on preliminary evidence of possible efficacy, this study will identify early signals of efficacy and

harm by evaluating key outcomes for Veterans with COVID-19 who have received and have not received CP treatment within the Veterans Health Administration (VHA) health care system.

### **2.3 Relevance to Veterans Health**

Preliminary studies on the COVID-19 epidemic show that being male, of increased age, and those who are infirm are disproportionately infected with the disease. This population is also thought to have increased risk of mortality and adverse outcomes. Many Veterans fit this profile, and the electronic health record (EHR) used to care for Veterans provides a unique opportunity to assess the morbidity and mortality for Veterans with COVID-19. CP is one of several novel therapies being used in the VHA. Veterans being treated with CP in VHA are tracked by the VA Pathology & Laboratory Medicine Service and the Mayo Clinic CP Registry. This study will provide the opportunity to observationally assess the impact of CP for all Veterans with COVID-19 using robust VHA data sources.

## **3.0 Aims**

We will assess the effect of CP therapy on 30-day mortality in COVID-19 patients early in the hospital course. We will emulate a hypothetical randomized trial (target trial) using observational data from a large national sample of patients who received care within the VA. We will create a VA-based cohort using VA Corporate Data Warehouse (CDW) data and other VHA healthcare data sources, such as the VA Pathology & Laboratory Medicine Service, combined with Mayo Clinic CP Registry data to evaluate the impact of CP among Veterans with COVID-19 on mortality and morbidity.

## **4.0 Resources and Personnel**

### **4.1 Organizational Structure**

The project is a collaboration between the CSP Epidemiology Centers (CSPEC) in Boston, MA and Seattle, WA. The organizational and administrative structure of this study will include the following components: (1) CSP Central Office; and (2) the CSPECs, represented by Boston and Seattle.

The Boston and Seattle CSPECs will share in the overall administrative coordination and oversight of the study. The Study Chairs, Drs. [name] and [name], will perform the scientific coordination of the study in conjunction with the Co-Investigators and CSPEC leadership.

## 5.0 Study Procedures

### 5.1 Study Design

This study is an observational study which emulates a hypothetical randomized trial (target trial) using observational data from the VHA EHR database. VA data will be used to emulate the eligibility criteria, treatment strategies, outcome, and follow-up of the target trial.

The specifications of the hypothetical trial are as follows. Patients would include Veterans hospitalized at a VA facility with a first-ever SARS-CoV-2 positive test within 7 days of admission, oxygen saturation of  $\geq 90\%$  within the past day, and non-severe COVID-19. Patients previously treated with convalescent plasma or residing in long-term care in the past 90 days would not be eligible. The patient would become eligible at the first SARS-CoV-2-positive test date (if the positive test occurred during hospitalization) or at the hospital admission date (if the positive test occurred before hospitalization). Eligible patients would be randomly assigned to either receive or not receive CP within 2 days of assignment. The primary outcome is 30-day mortality.

This retrospective data collection study will be conducted at the CSPECs within the VA Boston and VA Puget Sound health care systems. This project will access VA healthcare data in the EHR at a national level. Data will be identified and captured using CPRS, on VHA servers and the CDW using VINCI servers. Approved study staff will have access to the VINCI data mart to identify Veterans with positive SARS-CoV-2 testing.

If necessary, data can be extracted from medical records. In this case, data from VINCI/CDW will be reviewed by study staff and entered into a VA REDCap database. Each subject will be assigned a unique study ID and no PHI will be captured within VA REDCap. A crosswalk will be used to link the study ID to the Patient ICN. This document will be the only document to link study data and will be kept secure within the study's VINCI workspace and will only be accessible to a limited number of study staff conducting data review.

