## **5.4 Inclusion/Exclusion Criteria**

The population to study will include all Veterans who have tested positive for SARS-CoV-2 and treated for COVID-19 within the VHA healthcare system. Data available in the VA CDW will be utilized. Data analyses will assess multiple domains at the inpatient and outpatient level and obtained through the central VA COVID-19 Shared Data Resource. Domains for Data Analysis will include, but not limited to, Initial Presentation, Prior Medical Diagnoses, Health Limitations and Habits, Current Medications, Hospital Admission and Lab, Hospital Course, and Post Discharge Course. Data review will begin from date of diagnosis, short- and long-term outcomes will be assessed up to 1-year following diagnosis. There are no exclusion criteria for this study.

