### **Outcome variables**

The primary outcome is 30-day all-cause mortality.

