flexibly modeled using restricted cubic splines and estimated weights truncated at the 99.9th percentile to prevent extreme weights from affecting the analyses. In a secondary analysis, the adjustment for these covariates will instead be carried out via standardization. In all analyses, we use nonparametric bootstrapping, which yields unbiased estimates of standard error, to calculate percentile-based confidence intervals (CI) for survival difference and hazard ratio estimates.

Combined analysis with other cohorts in the Mayo Clinic CP Registry: Other health systems in the registry will be performing similarly data analyses. Research groups are encouraged to share the same data analysis plan. Some will contribute summary statistics to a research collaboration.

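### Patients already on comfort-only or hospice care at time zero remain eligible; they probably fall almost entirely in the no-CP group and would bias the result toward CP by an unknown amount

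*Combined protocol and SAP*

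**What the plan says.** Section 5.1 (Study Design) sets the target trial's entry conditions: "Patients would include Veterans hospitalized at a VA facility with a first-ever SARS-CoV-2 positive test within 7 days of admission", with oxygen saturation of at least 90% within the past day and non-severe COVID-19. The exclusions follow: "Patients previously treated with convalescent plasma or residing in long-term care in the past 90 days would not be eligible". Time zero is the first positive test if it came during the hospital stay, otherwise the admission date. The contrast is defined thus: "Eligible patients would be randomly assigned to either receive or not receive CP within 2 days of assignment".

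Section 5.4 (Inclusion/Exclusion Criteria) states: "There are no exclusion criteria for this study".

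On the outcome, section 5.6 says: "The primary outcome is 30-day all-cause mortality". For the per-protocol effect, its Statistical Analysis Plan would "adjust for the a priori baseline prognostic factors, as well as trial start day relative to first eligibility". On method: "The adjustment for these covariates would be carried out via inverse probability weighting", with "estimated weights truncated at the 99.9th percentile to prevent extreme weights from affecting the analyses". Standardization is a secondary analysis. The prognostic factors are not enumerated there.

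Hospice, comfort care, palliative care and code status appear in neither the eligibility text nor the covariate lists. The nearest listed item, discharge facility or outcome, is known only after baseline.

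**The concern.** A patient admitted from home with a comfort-measures-only order for, say, advanced cancer, who tests positive with adequate saturation, satisfies every condition in 5.1. The non-severe criterion describes the COVID-19 illness, not the patient's overall prognosis. The outcome is death from any cause, so that patient's death counts.

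Such a patient is unlikely to be given CP within 2 days and likely to die within 30. If the group is present in any number, the no-CP arm carries deaths that have almost no counterpart in the CP arm. The error then runs one way, toward an apparent benefit of CP, which is also the direction of the study's hypothesis.

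The plan already applies the same reasoning to sites: the Statistical Analysis Plan limits the target trial to centers where CP was in use. It does not apply it to patients.

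**Working it through.** **1. The plan's own figures.** The plan gives no figure for this group. Its power figures matter only for costing the fix, and they reproduce. I used a two-sided 0.05 test of two proportions with pooled variance, unexposed risk 0.25, and exposed risk 1 − 0.75^HR.

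| Groups | HR | Exposed risk | Power found | Power stated |
|---|---|---|---|---|
| 500 v 2,500 | 1.30 | 0.312 | 81.2% | 80% |
| 500 v 2,500 | 1.35 | 0.322 | 90.5% | 90% |
| 250 v 1,250 | 1.43 | 0.337 | 80.2% | 80% |
| 250 v 1,250 | 1.50 | 0.351 | 89.3% | 90% |

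The smaller groups follow from the stated design effect, 1 + (6 − 1) × 0.20 = 2.0, so 3,000/2 = 1,500.

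**2. Inputs for the bias.**
- From Sample Size/Power: 500 CP to 2,500 no-CP, so 1/6 on CP and 5/6 not; mortality about 25% among admitted patients who had died or been discharged, not restricted to non-severe disease.
- Assumed, because the documents give no figure: share c of eligible patients on comfort or hospice care at time zero, 1-5%; their 30-day mortality d, 50-80%; mortality m in everyone else, 25% or 10% (the latter for a non-severe cohort); none of them receives CP; CP has no effect.

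**3. Status left out of the weights.** The comfort-care share of the no-CP group is f = c/(5/6). The no-CP risk is (1 − f)m + f·d, the CP risk is m, and the risk ratio (RR) is their quotient.

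| m | c | d | f | No-CP risk | RR |
|---|---|---|---|---|---|
| 0.25 | 1% | 50% | 0.012 | 0.2530 | 0.99 |
| 0.25 | 3% | 80% | 0.036 | 0.2698 | 0.93 |
| 0.25 | 5% | 80% | 0.060 | 0.2830 | 0.88 |
| 0.10 | 1% | 50% | 0.012 | 0.1048 | 0.95 |
| 0.10 | 3% | 80% | 0.036 | 0.1252 | 0.80 |
| 0.10 | 5% | 80% | 0.060 | 0.1420 | 0.70 |

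The 5:1 ratio hardly matters. With 500 of about 4,000 admitted (1/8) on CP, the case m = 0.10, c = 3%, d = 80% has f = 0.03/(7/8) = 0.0343, no-CP risk 0.124 and RR 0.81.

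**4. Status included in whole-population weights.** Let e be the probability of CP in these patients. An untreated one gets weight 1/(1 − e), which tends to 1 as e approaches zero. A treated one would get 1/e, but few or none exist, and truncation would cut the weights of any who do. The weighted no-CP group then holds share c instead of f, and the CP group still holds none. At m = 0.10, c = 5%, d = 80%, the no-CP risk is 0.95 × 0.10 + 0.05 × 0.80 = 0.135 and RR = 0.74, against 0.70 with the status omitted. At m = 0.25 it is 0.95 × 0.25 + 0.05 × 0.80 = 0.2775 and RR = 0.90, against 0.88. Most of the distortion remains. Standardization would have to extrapolate a CP outcome for patients who never receive CP.

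**5. Power cost of excluding the group.** Hold no-CP mortality at 25%, and assume these patients are 5% of that group with 70% mortality. The remaining risk is (0.25 − 0.05 × 0.70)/0.95 = 0.2263. Power at HR 1.3 goes from 81.2% to 77.6% if 2,500 no-CP patients are still available, or 77.2% with 2,375.

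**The case against.** **Existing criteria narrow the group.** Non-severe disease, saturation of at least 90% and the long-term-care exclusion will remove some of these patients, and only orders in place at time zero count. The residual share may be small. At 1%, the table's two 50% cases give RR 0.99 and 0.95. This stands, and it is why the size cannot be asserted.

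**The larger figures rest on 10% mortality.** The only mortality figure in the documents is 25%, under which the whole assumed range gives 0.99-0.88. A lower risk in a non-severe cohort is plausible, since the 25% covers all admissions, but it remains an assumption. Both ranges have to be shown.

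**Stronger readings a reader might infer.**
- That these patients enter the no-CP arm only. The documents hold no data on CP use in them, and the target trial as written admits them. A very low probability of CP is a reasonable inference, not a documented fact.
- That weighting cannot correct the problem. The plan does not name the population its weights target. Weights aimed at the treated population, with this status measured, would give such patients almost no weight. The adjustment set is not enumerated and the variable list is described as not exhaustive, so this route is open, though nothing in the plan takes it.
- That the bias can exceed the plan's detectable effect, by comparing RR 0.70 with 1/1.3 = 0.77. That comparison fails. The 1.3 is a hazard ratio for harm at 25% mortality. The 0.70 corner has risks of 10% and 14.2%, which is a hazard ratio of ln(0.90)/ln(0.858) = 0.69. By the method in step 1, power there is about 73%, and the protective hazard ratio detectable with 80% power at 14.2% no-CP risk is about 0.66. The corner falls short of it.

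**Conclusion.** The point holds as a cheap improvement. The eligibility text is intact and admits patients who are on comfort-only or hospice care at time zero, and neither the covariate list nor the weighting as specified deals with them. If they seldom receive CP and often die, which is likely but not documented, the bias favors CP.

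Its size is unknown. Under the stated assumptions it runs from negligible (RR 0.99) to 0.88 at 25% mortality in other patients, and from 0.95 to 0.70 at 10%. The documents do not support saying that the result will be materially wrong, only that a one-directional source of error has been left open when one line would largely close it.

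**What to change.** - Add to the 5.1 eligibility criteria: exclude patients with a comfort-measures-only or hospice order, or hospice enrolment, recorded on or before time zero. Apply it identically whatever the patient's CP status. Do not use later orders, which would condition on events after baseline.
- Identify the status from encounter or diagnosis codes, or from the medical-record extraction that 5.1 already allows.
- Keep do-not-resuscitate status without comfort care as a baseline covariate, not an exclusion.
- Reconcile 5.4 with 5.1 in the same edit, since one denies and the other lists exclusions.

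Cost: one eligibility line, one derived variable, and slightly fewer no-CP patients and events; in the example above, about 4 points of power at HR 1.3. The result would not apply to patients on comfort care. The documents do not show that dated orders can be retrieved reliably, so capture may be incomplete and some of the bias may remain. Report how many patients the criterion removes.
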